### **11.6.2 Source Documentation**

The Investigator must keep accurate separate records (other than the eCRFs) of all subject visits, being sure to include all pertinent clinical study-related information. A statement should be made indicating that the subjects have been included in this clinical study and have provided signed written Informed Consent. All AEs must be thoroughly documented.

Results of any diagnostic tests conducted during the clinical study should also be included in the source documentation.

### **11.6.3 Archives**

All pertinent data, samples, photographs, correspondence, and reports, the original or amended clinical study protocol, and all other material relating to the clinical study will be maintained

 GALDERMA	Title 43USD1805 Clinical Study Protocol Dysport New Dilution GL	Doc id [REDACTED]
--	---	----------------------

securely in Sponsor/CRO/Investigator/Institution archives for the legally required duration for archiving.

The Investigator/Institution should maintain the essential clinical study documents as specified in Section 8 of ICH-GCP, and according to the applicable regulatory requirements.

The Investigator/Institution should take measures to prevent accidental or premature destruction of these documents.

If the Principal Investigator retires, relocates, or withdraws from the responsibility of keeping the clinical study records for any other reasons, custody must be transferred to a person who will accept the responsibility. The Sponsor/CRO must be notified in writing of the name and address of the new custodian.

## 11.7 Insurance

A certificate attesting Third Party coverage of CRO/Sponsor will be provided upon request.

## 11.8 Publication Policy

The Institution/PI's and the Sponsor's obligations regarding intellectual property rights, confidentiality, and publications are described in detail in the CTA.

a Defining the role of authors and contributors, compiled by the International Committee of Medical Journal Editors (ICMJE) (<http://www.icmje.org>).

 GALDERMA	Title 43USD1805 Clinical Study Protocol Dysport New Dilution GL	Doc id [REDACTED]
---	---	----------------------

Effective date: 2019-01-24 15:42

*Effective*

Version: 1.0

 GALDERMA	Title 43USD1805 Clinical Study Protocol Dysport New Dilution GL	Doc id [REDACTED]
---	---	----------------------

2019-01-24 15:42

Effective date:

*Effective*

Version: 1.0

 GALDERMA	Title 43USD1805 Clinical Study Protocol Dysport New Dilution GL	Doc id [REDACTED]
--	---	----------------------

Effective date: 2019-01-24 15:42

Effective date: 2019-01-24 15:42

*Effective*

[figure not shown]
Version: 1.0

 GALDERMA	Title 43USD1805 Clinical Study Protocol Dysport New Dilution GL	Doc id [REDACTED]
---	---	----------------------

Effective date: 2019-01-24 15:42

*Effective*

Version: 1.0

 GALDERMA	<small>Title</small> 43USD1805 Clinical Study Protocol Dysport New Dilution GL	<small>Doc id</small> [REDACTED]
---	--	-------------------------------------

Effective date: 2019-01-24 15:42

Effective date:

*Effective*

Version: 1.0

Title

43USD1805 Clinical Study Protocol Dysport New Dilution GL

Doc id

[REDACTED]

Effective date: 2019-01-24 15:42

*Effective*

Version: 1.0

 GALDERMA	Title 43USD1805 Clinical Study Protocol Dysport New Dilution GL	Doc id [REDACTED]
---	---	----------------------

Effective date: 2019-01-24 15:42

*Effective*

Version: 1.0

 GALDERMA	Title 43USD1805 Clinical Study Protocol Dysport New Dilution GL	Doc id [REDACTED]
---	---	----------------------

Effective date: 2019-01-24 15:42

*Effective*

Version: 1.0

	Title 43USD1805 Clinical Study Protocol Dysport New Dilution GL	Doc id [REDACTED]
--	---	----------------------

2019-01-24 15:42

Effective date:

4.2	[REDACTED]	24
Remote Spread or Hypersensitivity Preferred Terms	26
5.1	Remote Spread Preferred Terms	26
5.2	Hypersensitivity Narrow Standardized MedDRA Queries	27

List of Abbreviations

ADaM	Analysis Data Model
AE	Adverse Event
AESI	Adverse Event of Special Interest
ATC	Anatomical Therapeutic Class
BOCF	Baseline Observation Carried Forward
CHMP	Committee for Medicinal Products for Human Use
CMH	Cochran-Mantel-Haenszel
CRF	Case Report Form
CSR	Clinical Study Report
DBL	Database Lock
EDC	Electronic Data Capture
ET	Early Termination
FDA	Food and Drug Administration
GAIS	Global Aesthetic Improvement Scale
ICH	International Council on Harmonisation
ILA	Investigator Live Assessment
IND	Investigational New Drug
ITT	Intent-to-Treat
KM	Kaplan-Meier
MCMC	Markov Chain Monte Carlo
MedDRA	Medical Dictionary for Regulatory Activities
MI	Multiple Imputation
OC	Observed Case
PP	Per-Protocol
PT	Preferred Term
Q1	First Quartile
Q3	Third Quartile
SAP	Statistical Analysis Plan
SD	Standard Deviation
SDTM	Standard Data Tabulation Model
SMQ	Standardised MedDRA Query
SOC	System Organ Class
SSA	Subject Self-Assessment
TEAE	Treatment Emergent Adverse Event
U	Units
US	United States
VAS	Visual Analog Scale
WHODD	World Health Organization Drug Dictionary

1 Study Information

1.1 Background

This statistical analysis plan (SAP) describes the analysis variables and statistical procedures that will be used to analyze and report the results from Protocol 43USD1805 (v1.0), dated 24JAN2019.

The SAP was written in accordance with the recommendations outlined in the International Council on Harmonisation (ICH) E9 Guideline entitled “Guidance for Industry: Statistical Principles for Clinical Trials” and the ICH-E3 Guideline entitled “Guidance for Industry: Structure and Content of Clinical Study Reports”.

1.1.1 Study Design

This is a phase 3, multicenter, randomized, double-blind, placebo-controlled, United States (US) study to evaluate the efficacy and safety of a new dilution and injection volume of abobotulinumtoxinA for the treatment of moderate to severe glabellar lines.

1.1.2 Number of Subjects and Randomization

1.2 Study Objectives

The objective of this study is to evaluate the efficacy and safety of a single dose of a new dilution and injection volume of abobotulinumtoxinA compared to placebo in the treatment of moderate to severe glabellar lines.

1.2.1 Primary Efficacy Objective

The primary objective of this study is to evaluate the efficacy of a single dose of 50 U of abobotulinumtoxinA compared to placebo in the treatment of moderate to severe glabellar lines, based on the primary efficacy endpoint.

1.2.2 Secondary Efficacy Objectives

Term	Percentage
GMOs	85%
Organic	75%
Natural	88%
Artificial	35%
Organic	82%
Natural	89%
Artificial	40%
Organic	87%
Natural	90%
Artificial	50%

1.2.3 Exploratory Efficacy Objectives

1.2.4 Safety Objectives

The safety objective is to evaluate the safety of a single dose of 50 U of abobotulinumtoxinA compared to placebo in the treatment of moderate to severe glabellar lines.

1.3 Efficacy Assessments

For all assessments, baseline will be defined as the observation that is closest to but prior to study treatment on Day 0. Change from baseline will be calculated as the value at a given time point minus the baseline value.

1.3.1

11. **What is the primary purpose of the *Journal of Clinical Endocrinology and Metabolism*?**

Term	Percentage
GMOs	~10%
Organic	~85%
Natural	~75%
Artificial	~65%

1.3.2 [REDACTED]

Category	Value
1	Short
2	Medium
3	Very Long
4	Medium
5	Medium
6	Very Long

1.3.3 [REDACTED]

Term	Percentage
GMOs	~75%
Organic	~95%
Natural	~90%
Artificial	~75%
Organic	~95%
Natural	~90%
Artificial	~75%
Organic	~95%
Natural	~90%
Artificial	~75%

1.3.4 Subject Satisfaction Questionnaire

For more information, contact the Office of the Vice President for Research and Economic Development at [contact] or [contact].

1.3.5

1.3.6 Diary Card

Subjects will be asked to record their assessment of study treatment response in a diary card on Days 1 through 7. They will be asked to respond “Yes” or “No” to the following question: “Since being injected have you noticed an improvement in the appearance of your glabellar lines (lines between your eyebrows)?”

1.4 Efficacy Endpoints

1.4.1 Primary Efficacy Endpoint

The composite responder rate will be evaluated using the ILA 4-point Photographic Scale and the SSA Static 4-Point Categorical Scale of Glabellar Line Severity at maximum frown at Month 1. A composite responder is defined as a subject who achieves a score of 0 or 1 in glabellar line severity and at least 2 grades improvement from baseline on both scales concurrently.

1.4.2 Secondary Efficacy Endpoints

Secondary efficacy endpoints include:

- [REDACTED]

- [REDACTED]
- [REDACTED]
- [REDACTED]

1.4.3 Exploratory Efficacy Endpoints

Exploratory efficacy endpoints include:

1) [REDACTED]

3) [REDACTED]

[REDACTED]

[REDACTED]

[REDACTED]

[REDACTED]

[REDACTED]

1.5 Safety Assessments

The methods for collecting safety data are described in Section 7.2 of the Clinical Study Protocol.

1.6 Safety Endpoints

Safety endpoints include:

1) Treatment Emergent Adverse Events

Adverse events (AEs) are to be monitored throughout the course of the study. The study period for the purpose of AE collection is defined as the period from the signing of a study specific informed consent to study exit for a subject. AEs recorded on the electronic case report forms (CRFs) will be coded using the Medical Dictionary for Regulatory Activities (MedDRA) Version 22.0. AEs will be classified as treatment emergent adverse events (TEAEs) if the AE had an onset time greater than or equal to the time of the dose of study treatment.

AE endpoints include:

- Incidence,
- Causality (related/not related to investigational product),
- Intensity (mild/moderate/severe),
- Time to onset,
- Duration,
- Leading to study withdrawal,

- Seriousness.

2) Focused Physical Examination

At screening, baseline, Days 2 and 14, and Months 1 and 6, the Investigator or designee will perform a physical examination of the subject that includes the face and neck. The Investigator may choose to investigate any other sign that he/she observes during the physical examination and should assess all abnormal findings for clinical significance.

2 Statistical Methods

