### 7.2.2.1 *Definitions*

#### 7.2.2.1.1 *Adverse Events (AE)*

According to ICH E2A, an AE is any untoward medical occurrence in a patient or a clinical investigation subject administered a pharmaceutical product and which does not necessarily have a causal relationship with this treatment. An AE can therefore be any unfavorable and unintended sign (including an abnormal laboratory finding), symptom, or disease temporally associated with the use of a medicinal (investigational) product, whether or not related to the medicinal (investigational) product.

Thus any new sign, symptom or disease, or any clinically significant worsening of an existing sign, symptom or disease (including new episodes of a chronic disease [e.g., hay fever, allergy]) compared to the condition at the first visit, should be considered as an AE. Lack of efficacy is not considered as an AE.

Notes:

- There should be an attempt to report a diagnosis rather than the signs, symptoms or abnormal laboratory values associated with the report of an AE. However, a diagnosis should be reported only if, in the investigator's judgment, it is relatively certain. Otherwise, symptoms, signs, or laboratory values should be used to describe the AE.
- Pregnancy is not to be considered as an AE; however, is an important medical event that must be monitored as described in Section [7.2.2.3](#).
- The effects of Dysport and all BoNT products may spread from the area of injection to produce symptoms consistent with BoNT effects. These symptoms have been reported hours to weeks after injection. Remote spread of toxin that affects swallowing and breathing can be life threatening, and there have been reports of death. The risk of symptoms is increased in subjects who have underlying conditions (e.g. disorders of the neuromuscular junction) that would predispose them to these symptoms. Dysport is contraindicated in individuals with known hypersensitivity to any BoNT preparation or to any of the components in the formulation.

 GALDERMA	Title 43USD1805 Clinical Study Protocol Dysport New Dilution GL	Doc id XXXXXXXXXX
--	---	--

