#### 7.2.2.1.2 *Treatment Emergent Adverse Event (TEAE)*

A TEAE is an event that emerges during treatment, having been absent pre-treatment, or worsens relative to the pretreatment state.

Investigators are responsible for monitoring, recording, and reporting all AEs that occur during the study as described. TEAEs will be delineated from AEs following database lock.

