#### **7.2.2.2 Reporting Procedures**

##### **7.2.2.2.1 Procedures for Reporting Adverse Events**

The collection of AEs is from the time that a subject signs the ICF to their final visit.

At each post-enrollment visit, the Investigator (or sub-Investigator) will question the subject about AEs using an open non-persuasive question to elicit reporting of AEs, for example “Have you noticed any change in your health since the last visit?” Directed questioning and examination will then be performed as appropriate.

Any AE occurring during the AE reporting period, whether it is related to the study product or not, will be recorded immediately in the source document, and described on the AE form of the eCRF along with the date of onset, severity, relationship to the study product, and outcome, without omitting any requested and known information. Additional information will be requested under certain circumstances.

Adverse Events (AEs) assessed as related to the treatment or study procedure will be monitored until they have resolved or reached a stable condition. Other AEs will be monitored until the last visit if they have not resolved or reached a stable condition.

The Investigator will obtain and maintain in the subject’s files all pertinent medical records, information and medical judgment from colleagues who assisted in the treatment and follow-up of the subject. If necessary, the Investigator will contact the subject’s personal physician or hospital staff to obtain further details.

For SAEs (see Section [7.2.2.2.2](#)) and pregnancies (see Section [7.2.2.2.3](#)), the Sponsor is to be informed immediately by e-mail. The event must be reported by e-mail to the Safety Mailbox within 24 hours of receipt of the information (contact details in Section [7.2.2.2.2](#)).

Effective

Version: 1.0

 GALDERMA	Title 43USD1805 Clinical Study Protocol Dysport New Dilution GL	Doc id [REDACTED]
--	---	----------------------

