2.5.3 Adverse Events of Special Interest

Adverse events of special interest (AESIs) for abobotulinumtoxinA are TEAEs that suggest a possible remote spread of effect of the toxin or events suggestive of hypersensitivity like reactions. TEAEs due to possible remote spread of the effects of abobotulinumtoxinA will be identified using the list of MedDRA PTs compatible with the mechanism of action of abobotulinumtoxinA and based on the recommendations from the Committee for Medicinal Products for Human Use (CHMP) and the Food and Drug Administration (FDA). TEAEs potentially representing hypersensitivity reactions will be identified using the Standardised MedDRA Query (SMQ) (narrow search query) for hypersensitivity reactions. A list of MedDRA preferred terms, used to identify any potential AESI, is provided in Section 5.

All TEAEs identified using the search strategy described above will be medically evaluated during the study, before the database lock and unblinding (if applicable), by the sponsor to identify events which could possibly represent 'remote spread of effect of toxin', or which are suggestive of 'hypersensitivity reactions' due to study treatment administration. Cases will be excluded if they are confounded by presence of alternative clinical etiologies (medical history, concomitant medication or diagnosis which could account for the symptoms); if they are considered to be local effects instead of distant spread as judged by the site of injection; the time period between the last study treatment administration and event onset is not in accordance with the expected mechanism of action; or due to insufficient information/evidence to make an assessment. In order to perform the analysis, variables including alternative etiology (medical history, concomitant medication, or diagnosis which could account for the symptoms), location of Dysport administration, and temporal relationship to Dysport administration will be considered.

In the TFLs, only the final list of AESIs confirmed by the sponsor as "a possible remote spread event" or "hypersensitivity reactions" will be taken into account.

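### SAP 1.6 defines TEAEs by onset alone and omits the protocol's worsening limb, so a pre-dose AE that worsens after injection counts only if the site re-records it

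*SAP*

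**What the plan says.** Protocol 7.2.2.1.2 defines the term: "A TEAE is an event that emerges during treatment, having been absent pre-treatment, or worsens relative to the pretreatment state". The same section says that TEAEs are separated from other AEs after database lock.

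SAP 1.6 applies a single test. An AE is treatment emergent "if the AE had an onset time greater than or equal to the time of the dose of study treatment". No visible part of the SAP adds a worsening limb.

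On collection, protocol 7.2.2.2.1 says: "The collection of AEs is from the time that a subject signs the ICF to their final visit". AEs with onset before dosing can therefore be in the database. The same section asks for each AE to be described "along with the date of onset, severity, relationship to the study product, and outcome".

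On special-interest events, SAP 2.5.3 defines them as a subset of TEAEs and says: "All TEAEs identified using the search strategy described above will be medically evaluated during the study". It places this review before lock. Protocol 9.1.3.1 is wider: the sponsor screens all AEs for remote spread of toxin effect or hypersensitivity.

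**The concern.** Incidence and severity of TEAEs is a named safety endpoint (protocol 2.1.4, SAP 1.6), and the two documents define it differently. The SAP's precedence clause (SAP 2.1) does not clearly settle the matter. It covers the protocol's statistical sections, whereas the TEAE definition stands in Section 7, on study assessments.

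The events at issue are AEs already running at dosing that get worse after the injection. The protocol's second limb exists to capture these. Under the SAP, their status depends on how each site happens to record them. The same status decides whether the event is screened for remote spread, which protocol 1.4 lists as an identified risk of the product.

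**Working it through.** No arithmetic applies, because the documents give no rate of pre-dose AEs and no visible interval between consent and dosing. The check is to trace cases through the definitions.

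**Step 1. How would a post-dose worsening be recorded?** Protocol 7.2.2.1.1 counts as an AE "any clinically significant worsening of an existing sign, symptom or disease", judged "compared to the condition at the first visit, should be considered as an AE". There are two situations.

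- The condition was present at the first visit. A clinically significant worsening after dosing is an AE under this wording. If it is dated at the worsening, its onset is after dosing.
- The condition arose between the first visit and dosing. It is already an AE, because it is new relative to the first visit. The text does not say whether a further worsening after dosing is a second AE or the course of the first. The comparison point is the first visit, not the state just before dosing.

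No visible text tells sites to open a new record in the second situation.

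**Step 2. Classify each case.**

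| Case | TEAE, protocol 7.2.2.1.2 | TEAE, SAP 1.6 | In SAP 2.5.3 search |
|---|---|---|---|
| A. New symptom after injection | Yes | Yes | Yes |
| B. Starts between consent and dosing, worsens after dosing, stays one record | Yes (worsening limb) | No | No |
| C. As B, but the worsening is entered as a new AE | Yes | Yes | Yes |
| D. Starts before dosing, no worsening afterwards | No | No | No |

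The documents disagree only in case B. B and C are the same clinical event and differ only in how the site recorded it.

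**Step 3. The special-interest pool.** Under protocol 9.1.3.1, case B is screened because all AEs are. Under SAP 2.5.3 it is not. Protocol 9.1.3.1 is a statistical section, so under SAP 2.1 the narrower SAP pool would prevail.

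**Step 4. Timing.** SAP 2.5.3 needs TEAEs to be identified and reviewed before lock. Protocol 7.2.2.1.2 has them delineated after lock. The two statements need reconciling.

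**Step 5. Day 0.** SAP 1.6 compares onset time with dose time. The protocol's list of AE items names a date of onset. The imputation rules in SAP 2.5.2 return dates and are stated for time to onset and duration, not for TEAE status. No visible rule classifies a Day 0 AE that has no onset time.

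**The case against.** The case on the other side has four parts.

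1. *Worsening is already an AE.* Protocol 7.2.2.1.1 says so, and SAP 1.5 takes its collection methods from protocol Section 7.2. A worsening entered with its own post-dose date passes the SAP rule. This stands. A reader might infer that pre-dose AEs aggravated by the injection can never become TEAEs, and the documents do not support that. What remains is case B, where the recording is left open.

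2. *The events are not lost.* The SAP 2.5.2 overview covers all AEs, and related AEs are tabulated by maximum intensity. This also stands. A reader might infer that the comparison of active with placebo is biased toward no difference. That is not shown. The visible AE tables are not restricted to TEAEs, no inferential safety analysis is planned, and such a bias would require more worsening on active than on placebo. The only visible analysis confined to TEAEs is the special-interest review.

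3. *Many case B events would be excluded from special interest anyway.* SAP 2.5.3 drops cases with an alternative etiology or implausible timing, and a symptom present before injection may often fail on those grounds. This is fair, but those exclusions are medical judgements made case by case. The onset rule removes the event before anyone looks at it.

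4. *The eCRF may collect onset time.* It is not visible, and protocol 7.2.2.2.1 asks for all requested information. A reader might infer that Day 0 events cannot meet the SAP rule. The documents do not establish that. They show only that no rule is stated for a missing time.

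**Conclusion.** The mismatch is real. SAP 1.6 narrows a protocol-defined safety endpoint, and SAP 2.5.3 carries the narrower definition into the special-interest review. The effect is confined to AEs that begin between consent and dosing, worsen after dosing and stay on one record. Those events remain in the all-AE tables.

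The number affected cannot be estimated. A reader might assume that 2–5% of subjects have a pre-dose AE and that 10–20% of those worsen. That gives 0.02 × 0.10 = 0.2% to 0.05 × 0.20 = 1.0% of subjects, which could then be compared with the 0.1% to <1% band that protocol 1.4 uses for uncommon ocular events. Neither input comes from the documents. The comparison also sets AEs of every kind against a band for particular ocular events. It should not be used.

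The conclusion assumes that no recording convention is given in material not visible here, such as an eCRF completion guide. It is a consistency defect that should be corrected because correction is cheap, not because a large effect has been shown.

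**What to change.** 1. **Definition and recording.** Replace the SAP 1.6 rule with: *A TEAE is an AE with onset at or after study treatment, or an AE with onset before treatment that worsens after treatment.* Pair it with one convention in the eCRF completion instructions: a post-dose worsening of a pre-dose AE is entered as a new AE dated at the worsening, and the original record is not also flagged as a TEAE. Both parts are needed. The definition alone requires the date of the worsening, and flagging both records would count the event twice in the event totals of SAP 2.5.2.

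2. **Special-interest search.** Run the SAP 2.5.3 search on all AEs, as protocol 9.1.3.1 states, before database lock. Reconcile this with the statement in protocol 7.2.2.1.2 that TEAEs are delineated after lock.

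3. **Day 0.** State that an AE dated on the day of treatment without a recorded onset time is treated as a TEAE unless it is known to have started before the injection.

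The cost is a SAP amendment, which SAP 2.1 provides for before lock, one recording instruction to sites and a protocol clarification on timing. The TEAE count rises slightly, and a few more AEs go to special-interest review.

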#### **6.3.4 Treatment Compliance Management and Record**

The treatment is an injection administered by the Investigator. It will be recorded in the eCRF that the injection has been administered. No other measurements of treatment compliance will be made.

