#### **Reasonable Possibility:**

According to the reporting Investigator, there is a reasonable possibility (i.e., suggestive evidence or arguments) that there is a causal relationship irrespective of the dose administered between:

- The study product (active or placebo) and the AE.
- The clinical study protocol procedure (e.g., bruising or marks from blood draws, injection related trauma, etc.) and the AE.

 GALDERMA	Title 43USD1805 Clinical Study Protocol Dysport New Dilution GL	Doc id [REDACTED]
--	---	----------------------

2019-01-24 15:42

Effective date:

A two-point scale (Yes or No response) shall be used for the causality assessment. The Investigator shall be asked to indicate a response to each of the following questions in the eCRF:

- “Do you consider that there is a reasonable possibility that the event may have been caused by the study product?”, and
- “Do you consider that there is a reasonable possibility that the event may have been caused by the study product injection procedure?”

If any of these questions is answered Yes, the AE is considered related.

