### **No Reasonable Possibility:**

No suggestive evidence or arguments can be identified regarding a causal relationship between the study product or the clinical study protocol procedure and the AE.

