### 9.1.3.1 *Safety Analysis*

AEs will be summarized descriptively by treatment group, SOC and PT using number and percentage of subjects with at least one event and number of events. The results will be further broken down by other factors such as severity, causality, seriousness, and whether the event led to discontinuation. Duration and time to onset of related AEs will also be presented by treatment group, SOC and PT.

The numbers and percentages of subjects with abnormalities in physical examination will also be summarized. The results of the urine pregnancy tests will be listed.

All AEs will be monitored by the Sponsor to determine if they meet the criteria of remote spread of effect of the toxin or hypersensitivity. A list of preferred terms for these types of events will be provided in the SAP, and will be further analyzed to determine if there is a plausible possibility that they represent distant spread of toxin or hypersensitivity. In order to perform the analysis, variables including alternative etiology (medical history, concomitant medication, or diagnosis which could account for the symptoms), location of Dysport administration, and temporal relationship to Dysport administration will be considered by the Sponsor.

 Title **43USD1805 Clinical Study Protocol Dysport New Dilution GL** Doc id XXXXXXXXXX

Effective date: 2019-01-24 15:42

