2.5.2 Adverse Events

A summary of all AEs (number and percentage of subjects with at least one event and number of events) by treatment group will be provided, which will include:

- Subjects with at least one AE (in total as well as serious AEs).
- Subjects with at least one treatment-related AE (in total as well as serious AEs).
- Subjects with at least one mild, moderate or severe treatment-related AE (in total as well as serious AEs).
- Subjects with at least one unrelated AE (in total as well as serious AEs).
- Subjects with at least one mild, moderate or severe unrelated AE (in total as well as serious AEs).
- Subjects with at least one AE that led to discontinuation (in total as well as serious AEs).
- Number of subjects who did not have an AE.

All other adverse event tables will also be summarized by treatment. Treatment-related AEs, as well as AEs unrelated to study treatment will be summarized by System Organ Class (SOC), PT and maximum intensity.

In addition, for treatment-related AEs, the number of days to onset and the duration of event will be summarized by SOC and PT.

- Time to onset of an AE will be derived as the start date minus the date of the most recent treatment. If the start date is missing, it will be assumed that the AE started on the day of the most recent treatment. If the start month is available but not the day, it will be assumed that the AE started on the first day of the month.
- Duration of an AE will be derived as the stop date minus the start date + 1. If the start date is missing, it will be assumed that the AE started on the day of most recent treatment. If the start month is available but not the day, it will be assumed that the AE started on the first day of the month. If the stop month is available but not the day, it will be assumed that the AE stopped on the last day of the month. Completely missing stop dates will not be imputed and therefore no duration will be calculated in these cases.

AEs that led to discontinuation from the study will also be summarized.

Serious AEs and treatment-related AEs with late onset (i.e. AEs with onset > 21 days after treatment) will be listed.

For subject counts, a subject will only be counted once per SOC and once per PT in cases where multiple events are reported for a subject within SOC or PT. For event counts, subjects with multiple events in a category will be counted for each event.

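### Does the SAP's product-only causality wording take injection-procedure events out of the related adverse events?

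*SAP*

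**What the plan says.** Protocol 7.2.2.1.7 has the investigator answer two yes/no questions for each adverse event: could the study product have caused it, and could the injection procedure have caused it. The combining rule follows directly: "If any of these questions is answered Yes, the AE is considered related". The opposite category is defined in the same section as no evidence of a "causal relationship between the study product or the clinical study protocol procedure and the AE", so it covers product and procedure together.

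SAP 1.6 lists the adverse event endpoints. One item reads "Causality (related/not related to investigational product"). SAP 2.5.2 specifies the tables and uses the terms treatment-related and unrelated throughout, for example: "In addition, for treatment-related AEs, the number of days to onset and the duration of event will be summarized by SOC and PT". It does not map these terms to the two eCRF answers. The matching sentence in protocol 9.1.3.1 speaks simply of related events: "Duration and time to onset of related AEs will also be presented by treatment group, SOC and PT".

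SAP 1.5 refers back to the protocol: "The methods for collecting safety data are described in Section 7.2 of the Clinical Study Protocol". SAP 2.1 gives the SAP precedence over the protocol, but only over its statistical sections.

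**The concern.** The only causality wording in the readable SAP names the product alone. A programmer who took it as a derivation would use the first eCRF question and ignore the second. Events attributed to the injection but not to the toxin would then move from the treatment-related tables to the unrelated ones and drop out of the onset and duration summaries, against the protocol rule.

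The word treatment does not clearly settle the matter. Protocol 6.3.4 says "The treatment is an injection administered by the Investigator", which takes in the injection. Protocol 7.2.2.2.1 says that events "assessed as related to the treatment or study procedure will be monitored" until resolved or stable, which sets treatment and procedure apart.

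The affected category is plausible in this trial. The protocol names injection trauma as an example of a procedure-caused event, its risk section lists injection site reactions among the most frequent related events in earlier trials, and the study examines a larger injection volume. At stake would be the absolute rate of related events in each arm, and whether two programmers would produce the same table from the same data.

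**Working it through.** The plan gives no figure to reproduce, so the check compares the two rules and traces which outputs depend on them.

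**Step 1: the four answer pairs.**

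| Product | Procedure | Protocol 7.2.2.1.7 | SAP 1.6 read literally |
|---|---|---|---|
| Yes | Yes | related | related |
| Yes | No | related | related |
| No | Yes | related | not related |
| No | No | not related | not related |

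The rules agree on 3 of 4 pairs and differ on 1, the procedure-only event.

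**Step 2: outputs that use the split.** The overview in SAP 2.5.2 has 7 rows. Four use it: treatment-related, treatment-related by severity, unrelated, unrelated by severity. Three do not: any event, events leading to discontinuation, subjects with no event. The tables by system organ class, preferred term and maximum intensity also use it, as do the onset and duration summaries and the listing of late-onset treatment-related events.

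**Step 3: size.** The literal related set is contained in the protocol related set. For the proportion of subjects with at least one related event,

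literal rate = protocol rate − p,

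where p is the proportion of subjects whose only protocol-related events are procedure-only. The documents give no value for p. It can lie anywhere from 0 to the whole protocol rate.

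This one-way result does not extend to the maximum-intensity cells. Suppose a subject has a severe procedure-only event and a mild product-related event in the same system organ class. The protocol rule counts that subject as severe and the literal rule as mild, so the mild count rises.

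**Step 4: which rule governs.**

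- The precedence clause in SAP 2.1 reaches only the protocol's statistical sections. Section 7.2.2.1.7 belongs to the safety assessment chapter, so its rule is not superseded.
- SAP 1.5 sends the reader to protocol section 7.2 for the collection of safety data. The two questions and the combining rule are both there.
- Protocol 7.2.2.2.1, in listing what goes on the adverse event form, also names relationship to the study product only. It does so alongside the two-question rule and plainly does not repeal it. The same short form in SAP 1.6 is weak evidence that a different rule was intended.
- SAP 1.6 is a list of endpoints, with neighbouring items as brief as incidence, duration and seriousness. The outputs are specified in SAP 2.5.2, whose term is treatment-related, not product-related.
- The contrast between treatment and study procedure in protocol 7.2.2.2.1 does not show that treatment excludes the injection. The protocol's examples of study procedures include blood draws, so the term is wider than the injection, whereas the second eCRF question concerns the injection procedure alone.

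Read together, the documents contain one explicit combining rule and no competing one.

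**The case for a change.** The best case for a change is that a SAP should define the flag on which several of its tables rest. SAP 1.5 refers to the protocol for how safety data are collected, which is not the same as how an analysis variable is derived. The limit on the precedence clause means that the SAP does not override the protocol rule, but the SAP does not expressly adopt it either. Independent programming checks agreement with the plan and cannot supply a derivation that the plan leaves out. Section 2.5.2 reads as complete, so redaction does not account for the gap. The remedy would be one sentence, using data already collected.

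Much of this stands as description: the term is undefined in the readable SAP, and a cross-reference would be good drafting. What does not stand is the step from an undefined term to a contradiction. To reach the discordant result, an analyst would have to treat a parenthesis in an endpoint list as a derivation and set aside an explicit protocol rule that remains in force. The proposed sentence would restate that rule and would not change any analysis the documents, read together, call for.

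**Conclusion.** No change to the plan is needed. This is a missing cross-reference that an analyst holding both documents fills sensibly: related means Yes to either question, unrelated means No to both.

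If the literal reading were programmed after all, the effect would be confined to the descriptive related/unrelated outputs. The overall related rate would fall by p, which is unknown and may be zero, and maximum-intensity cells could move either way. Total, serious and discontinuation counts would be the same. Events of special interest would also be unaffected, because SAP 2.5.3 identifies them by preferred terms and sponsor medical review. SAP 2.1.2 commits to listing all CRF data and derived variables, so procedure-only events would remain identifiable. SAP section 2.5 plans no inference on safety, and both products are administered identically, so the matter concerns the absolute related rate and not a test between arms.

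This rests on two assumptions: that both eCRF answers reach the analysis datasets, and that the table formats in the companion document, which was not available, do not impose a product-only rule.
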